#### The discontinuation criteria are:

- The participant withdraws consent to receive study intervention.
- The investigator believes that for safety or tolerability reasons (eg, AE) it is in the best interest of the participant to discontinue JNJ-3989 and PegIFN- $\alpha$ 2a.
- The participant becomes pregnant.
- The participant has a ≥grade 3 rash or allergic reaction.
- The participant has signs of hepatic decompensation (ie, clinical evidence of ascites, bleeding varices, or hepatic encephalopathy) or an increase in direct bilirubin >1.5x ULN in combination with INR ≥1.5x ULN or albumin <3.0 g/dL. Treatment with JNJ-3989 should be discontinued and alternative treatment options (outside the study) should be considered in discussion with the Sponsor.
- The participant has a confirmed ≥grade 3 eGFRcr abnormality.
  - If eGFRcr is not confirmed by eGFRcys, or not considered at least possibly related to JNJ-3989 or PegIFN- $\alpha$ 2a, or resolved after changing tenofovir disoproxil to TAF (if the patient was receiving tenofovir disoproxil), treatment with JNJ-3989 or PegIFN- $\alpha$ 2a can be continued after discussion with the sponsor.
- The participant has a QTcF prolongation (defined as a QTcF value of >500 ms, or an increase from baseline of >60 ms) at any given time point.
- The participant requires ≥7 days of treatment with any of the disallowed medications listed in Section 6.5 and does not intend to discontinue treatment with the disallowed medication.
- The participant has confirmed HBV virologic breakthrough (ie, confirmed on-treatment HBV DNA increase by >1 log10 IU/mL from nadir or confirmed on-treatment HBV DNA level >200 IU/mL in participants who had HBV DNA level <LLOQ of the HBV DNA assay). In case of virologic breakthrough, the same assessments will be done at an unscheduled visit as will be done in case of an ALT flare, but no PBMC sample will be taken (see Section 8.3.6.2 and Schedule of Activities).

If virologic breakthrough occurs during JNJ-3989 and PegIFN- $\alpha$ 2a administration, this does not automatically lead to stop of JNJ-3989 and/or PegIFN- $\alpha$ 2a, but should be assessed/discussed with the Sponsor.

In case of virologic breakthrough, a viral sequencing sample will be collected at the next visit.

- The participant has ALT/AST elevations, as described in Section 8.3.6.2, Intervention-emergent ALT/AST Elevations.
- The participant has confirmed ≥Grade 3 hematologic abnormalities as described in Section 8.3.6.4, Hematologic abnormalities.

*Note:* The grades are based on the DAIDS Toxicity Grading Scale (see Section 10.9, Appendix 9, DAIDS Table).

In addition, PegIFN- $\alpha$ 2a during consolidation phase must immediately be discontinued for any of the following reasons:

- Participant has platelet count <25,000 cells/mm^3
- Participant has ANC <500 cells/mm^3 Note: PegIFN-α2a treatment can be restarted when ANC values return to more than 1,000 cells/mm^3 (see details in Section 6.6, Dose Modification)
- Participant develops evidence of hepatic decompensation during treatment, or ALT increase clinically significant or accompanied by direct bilirubin increase
- Participant develops thyroid disorders or diabetes during treatment and cannot be controlled with medication
- Participant develops new or worsening ophthalmologic disorders
- Participant develops any deterioration of cardiovascular status
- Participant develops serious, acute hypersensitivity reaction (e.g., urticaria, angioedema, bronchoconstriction, anaphylaxis)
- Participant develops serious infection (bacterial, viral, fungal) and sepsis
- Participant develops persistent or unexplained pulmonary infiltrates or pulmonary function impairment
- Participant with onset or worsening of psoriatic lesion
- Participant develops moderate or severe depression, or other psychiatric symptoms (for mild depression, treatment discontinuation may be considered)

*Note:* Participants who develop a neuropsychiatric AE during PegIFN- $\alpha$ 2a treatment, will be monitored closely until the neuropsychiatric AE resolves, with frequent (at least weekly) follow-up phone calls.

- Participant develops colitis symptoms (such as but not limited to abdominal pain, bloody diarrhea, and fever)
- Participant develops symptoms or signs suggestive of pancreatitis

For participants who prematurely discontinue PegIFN- $\alpha$ 2a, treatment with PegIFN- $\alpha$ 2a may be restarted according to the recommendations from the locally approved prescribing information for PegIFN- $\alpha$ 2a.

If a participant prematurely (before the end of the consolidation phase) discontinues JNJ-3989, the participant will enter the 48-week follow-up phase and complete the follow-up schedule as per the Schedule of Activities, unless the participant withdraws consent. If a participant prematurely discontinues PegIFN-α2a (before the end of the consolidation phase), treatment with JNJ-3989 and NA should be continued as planned. In case the participant withdraws consent, NA treatment may be continued or, in consultation with the sponsor, discontinued based on investigator judgement or completed based on the NA treatment completion criteria (see Section 6.6).

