# 7.1. Discontinuation of Study Intervention

With the implementation of Protocol Amendment 6, all participants had to stop JNJ-6379 treatment immediately.

Treatment with JNJ-3989 and PegIFN- $\alpha$ 2a must be discontinued before consolidation Week 12 for all reasons listed in Section 7.1 of the Master Protocol PLATFORMPAHPB2001 and for all additional intervention-specific reasons. All the discontinuation criteria are listed below and the intervention-specific criteria are highlighted (colored fill). For the few criteria from the Master

Protocol that are specified or more restricted in this ISA, the changes compared to the Master Protocol are also highlighted (colored fill). If JNJ-3989 is discontinued, PegIFN- $\alpha$ 2a should also be discontinued. If PegIFN- $\alpha$ 2a is discontinued, JNJ-3989 should be continued. NA treatment may be continued or, in consultation with the sponsor, discontinued based on investigator judgement.

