# 8.1. Efficacy Assessments

All efficacy assessments will be performed at predefined time points as specified in the Schedule of Activities.

Qualitative and quantitative HBsAg and HBeAg, and quantitative HBcrAg as well as anti-HBs and anti-hepatitis B e (anti-HBe) antibodies will be determined using validated serologic assays in a central laboratory. Samples for the determination of HBsAg and HBeAg will be processed in real-time. Samples for the determination of HBcrAg can be analyzed in batch and at the sponsor's request.

HBV DNA and HBV RNA will be quantified at central laboratories using validated assays for the quantification of HBV DNA and HBV RNA. Samples for the determination of HBV DNA will be processed in real-time. Samples for the determination of HBV RNA can be analyzed in batch and at the sponsor's request.

Hepatitis B virus DNA, HBsAg, HBeAg, anti-HBs, and anti-HBe antibody testing results will be provided to the investigator and the sponsor from screening until the end of follow-up.

It is the responsibility of the investigator:

- To monitor HBV DNA results and ensure that JNJ-3989 and PegIFN-α2a are discontinued in participants with confirmed virologic breakthrough (see Section 7.1, Discontinuation of Study Intervention),
- To assess if NA treatment completion criteria are met (see Section 6.6, Study Intervention Completion at Consolidation Week 12),
- To assess whether restart of NA treatment during follow-up is needed (see Section 6.6.2, NA Re-treatment Criteria and Monitoring After Stopping of NA).

In participants enrolled at a site with an on-site Fibroscan device, Fibroscan assessments will be performed at different time points to determine changes in fibrosis levels.

Samples may be used by the sponsor for additional exploratory assessments analyzing the serologic and virologic characteristics of HBV infection and efficacy or safety of the study intervention.

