## 8.3.6.2. Intervention-emergent ALT/AST Elevations

Elevated liver enzyme activity can be triggered by the underlying HBV disease as well as by the study intervention.

Management of intervention-emergent ALT/AST elevations is presented graphically in Section 10.6, Appendix 6, Intervention-emergent ALT/AST Elevations and is described below.

Any intervention-emergent elevation of ALT and/or AST ≥3x ULN and ≥3x nadir (ie, lowest value during study participation) should trigger an assessment of confounding factors (alcohol intake, change in concomitant medication, and comorbidities) and should trigger a confirmatory study visit to repeat laboratory testing of AFP, ALT, AST, ALP, bilirubin (total and direct), INR, albumin, and HBV DNA. Additional tests should be considered based on clinical judgement (Refer to Section 10.6, Appendix 6, Intervention-emergent ALT/AST Elevations). The confirmatory visit should be scheduled as soon as possible, preferably within 7 days of the receipt of the initial ALT/AST results. In case the repeat laboratory testing shows an isolated ALT/AST elevation (ie, with stable albumin, bilirubin [total and direct], and INR) the participant may continue study intervention. In case of confirmed ALT elevation >1,000 U/L and ≥3x the baseline value, JNJ-3989 and PegIFN-α2a should be discontinued unless dynamics of the ALT elevation are indicating improvement towards resolution of the flare. In both cases, NA treatment should be continued. The participant will be monitored (laboratory testing of ALT, AST, ALP, bilirubin [total and

direct], INR, albumin, and HBV DNA) on a weekly basis until ALT and AST levels have returned to <5x ULN and HBV DNA is <20,000 IU/mL.

If the ALT and/or AST level is  $\ge 3x$  ULN and  $\ge 3x$  nadir and is associated with any of the following laboratory results or clinical symptoms:

- INR  $\geq$ 1.5, OR
- direct bilirubin >1.5x ULN, OR
- serum albumin <3.0 g/dL, OR
- ascites, hepatic encephalopathy, or liver-related symptoms (eg, severe fatigue, nausea, vomiting, right upper quadrant pain in the absence of an alternative medical explanation), OR
- other indication of reduced liver function

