## 8.3.6.4. Hematologic Abnormalities

Mild thrombocytopenia was observed in recently conducted non-clinical toxicology studies with the combination of JNJ-3989 and JNJ-6379. In addition, in a 3-month combination study with 80 rats, 1 rat developed pancytopenia related to bone marrow depletion after 23 days of dosing. Previously, in a 9-month dog study in 24 dogs treated with JNJ-6379 alone, pancytopenia which correlated with a marked increase in plasma cell-like cells in the bone marrow was observed in 1 dog after 60 days of dosing.

No thrombocytopenia or pancytopenia has been observed in the ongoing Jade study (56136379HPB2001) investigating JNJ-6379/Placebo with or without NA treatment. All 232 participants have completed at least 24 weeks of study intervention. In the Phase 1/2a AROHBV1001 study with JNJ-3989, mild transient thrombocytopenia (Grade 1) was observed in 6 out of 84 participants receiving 3 SC injections of JNJ-3989 alone over a period of up to 12 weeks with background of NAs. The transient thrombocytopenia was not considered clinically significant. No thrombocytopenia or pancytopenia was observed in 12 participants when JNJ-3989 and JNJ-6379 were given in combination over a 12-week period.

Based on the non-clinical findings, any relevant abnormalities in hematologic parameters will be carefully monitored as described below:

- Platelet counts: <100,000 cells/mm^3 or <100 GI/L or reduction from baseline by at least 50%
- Hemoglobin: Decrease of at least 2 g/dL from baseline or at least Grade 2 (DAIDS)
- Reticulocytes: Reduction to <0.5% of the RBC count
- Neutrophil count: Treatment emergent reduction to at least Grade 2 (DAIDS)

In case any one of the above criteria are met, a confirmatory visit should be scheduled as soon as possible, preferably within 7 days of the receipt of the initial results. Confirmation of the results will trigger weekly or biweekly (every other week) unscheduled visits until improvement or stabilization of the respective parameter(s). Stabilization is defined as no further significant reduction over two consecutive visits.

In case of confirmed Grade 3 or Grade 4 hematologic abnormalities, discontinuation of treatment with JNJ-3989 and PegIFN- $\alpha$ 2a should be considered. In case of discontinuation, NA treatment should be continued.

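### Protocol 7.1 makes confirmed Grade 3 or higher hematologic abnormalities a mandatory stop, but the section it cites (8.3.6.4) makes stopping discretionary, and Table 4 and Section 8.1 add further mismatches

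*Protocol*

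**What the plan says.** Section 7.1 opens by stating that JNJ-3989 and PegIFN-α2a "must be discontinued before consolidation Week 12 for all reasons listed in Section 7.1 of the Master Protocol PLATFORMPAHPB2001" and for all additional intervention-specific reasons, and that every criterion is listed below. Eleven criteria follow. The last is: "The participant has confirmed ≥Grade 3 hematologic abnormalities as described in Section 8.3.6.4, Hematologic abnormalities".

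Section 8.3.6.4 names the parameters (platelets, hemoglobin, reticulocytes, neutrophils) and how a finding is confirmed. It then says that for confirmed Grade 3 or Grade 4 abnormalities "discontinuation of treatment with JNJ-3989 and PegIFN- $\alpha$ 2a should be considered".

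Two other criteria in the list carry a written exception. For eGFR, treatment "can be continued after discussion with the sponsor" under stated conditions. For virologic breakthrough during dosing, "this does not automatically lead to stop of JNJ-3989 and/or" PegIFN-α2a, and the case goes to the sponsor. Section 8.1 makes investigators responsible for ensuring that both drugs "are discontinued in participants with confirmed virologic breakthrough (see Section 7.1, Discontinuation of Study Intervention", with no qualifier.

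Section 6.6 Table 4 gives PegIFN-α2a dose steps by ANC and platelet count, as an example taken from prescribing information. A second list in 7.1 requires PegIFN-α2a alone to stop at once at platelets below 25,000 or ANC below 500, with restart allowed once ANC exceeds 1,000. Section 7.1 also says JNJ-3989 continues when PegIFN-α2a is stopped, and that PegIFN-α2a stops when JNJ-3989 does.

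**The concern.** One confirmed laboratory value cannot be both a mandatory and a discretionary stop. An investigator who reads 7.1 stops both drugs. One who follows its cross-reference to 8.3.6.4 weighs the decision and may continue. Both have followed the protocol.

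Hematologic abnormalities are an event of special interest (8.3.6), and PegIFN-α2a is associated with platelet decreases (2.2.2.3), so this is first a matter of participant safety. Four further consequences follow:

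- Stopping JNJ-3989 also stops PegIFN-α2a and sends the participant to follow-up, so the reading decides whether the regimen is completed.
- The SAP 6.1.2 table of treatment-emergent adverse events leading to discontinuation would partly reflect which section each site followed.
- ITT membership needs at least one consolidation-phase dose (Protocol 9.3, SAP 2.3). A stop during induction removes the participant from ITT. Continuing into consolidation keeps the participant in.
- SAP Attachment 1 sequence 58 covers a participant who met a discontinuation criterion but did not stop. It is marked as a per-protocol exclusion without the condition, found on many other rows, that the deviation be classed as major.

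**Working it through.** The plan states no figure to reproduce, so the passages are set side by side for confirmed values. Grades come from Protocol Appendix 9 (participants older than 7 days); counts are in cells/mm³.

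| Confirmed value | DAIDS grade | 7.1 main list | 8.3.6.4 | PegIFN-α2a provisions |
|---|---|---|---|---|
| Platelets 25,000 to <50,000 | 3 | stop both | weigh stopping both | reduce dose (Table 4) |
| Platelets <25,000 | 4 | stop both | weigh stopping both | stop PegIFN-α2a (Table 4; 7.1 PegIFN-only list) |
| ANC 500–599 | 3 (range 400–599) | stop both | weigh stopping both | reduce dose (Table 4, ANC <750) |
| ANC <500 | 3 (400–499) or 4 (<400) | stop both | weigh stopping both | stop PegIFN-α2a; restart allowed above 1,000 |

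In rows 1 and 3 one value meets three different instructions for PegIFN-α2a. In row 4 the restart note and the main list differ once the value is confirmed. In rows 2 and 4, 7.1 continues JNJ-3989 when PegIFN-α2a alone is stopped, while its main list stops both. During induction PegIFN-α2a is not given, so only the 7.1 versus 8.3.6.4 conflict on JNJ-3989 arises.

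**Breakthrough.** Section 7.1 states a rule and then an exception. Section 8.1 repeats the rule without the exception, though it cites 7.1.

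**How many participants.** The documents give no rate of confirmed Grade 3–4 hematologic abnormality on this regimen. Assume p = 2%, 5% or 10%, purely for illustration. With n = 33 (Cohort 2) or about 60 (both cohorts), the expected number is n × p and the chance of at least one case is 1 − (1 − p)^n.

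| p | n = 33: expected | n = 33: at least one | n = 60: expected | n = 60: at least one |
|---|---|---|---|---|
| 2% | 0.66 | 49% | 1.2 | 70% |
| 5% | 1.65 | 82% | 3.0 | 95% |
| 10% | 3.3 | 97% | 6.0 | 99.8% |

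**Effect on a proportion.** Assume 30 evaluable participants (the planning figure) and one responder. The second assumption is prompted by SAP Amendment 4, which reports a single participant who met the NA completion criteria and stopped NA at consolidation Week 12. Removing one non-responder moves 1/30 = 3.33% to 1/29 = 3.45%, a change of 0.11 percentage points. Only removal of the responder would matter visibly (0/29 = 0%).

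**The case against.** The best defence is that the words *as described in* import the softer rule: 7.1 names the topic and 8.3.6.4 supplies the handling. The ALT/AST criterion has the same form ("The participant has ALT/AST elevations, as described in Section 8.3.6.2, Intervention-emergent ALT/AST Elevations"), and its cited section says that with an isolated elevation on repeat testing "the participant may continue study intervention". The hematology criterion does depend on 8.3.6.4 for its parameters and for what confirmation means, so it would be wrong to say that it states its own complete trigger. That much stands.

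It does not settle the matter. The lead-in makes every listed criterion mandatory. The hematology criterion adds its own grade threshold, and 8.3.6.4 attaches a discretionary action to exactly that threshold. Where 7.1 intends discretion for eGFR and breakthrough, it says so in place.

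A reader might also infer that 7.1 contradicts itself on breakthrough. It does not: the exception follows the rule directly, and the Amendment 5 history shows that guidance on continuing treatment was added deliberately. Only the unqualified duty in 8.1 is out of line, and its reference to 7.1 and the sponsor discussion limit the harm.

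Nor do the immediate PegIFN-only cut-offs contradict the main list in themselves, since they act without confirmation. The overlap arises only once the value is confirmed.

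Finally, the safety tables are descriptive, an investigator may stop for safety under either reading, and the SAP already lists Grade 3 or higher events and events of special interest. So variation in the discontinuation table could not be attributed to this wording alone. But Appendix 9 notes that a laboratory abnormality need not be an adverse event, so those adverse event listings may miss some confirmed low counts.

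**Conclusion.** The conflict between 7.1 and 8.3.6.4 is on the face of the text and should be fixed. Table 4 and the restart note add different PegIFN-α2a instructions for the same counts. The mismatch between 8.1 and 7.1 on breakthrough is secondary.

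The number of participants affected is probably small. That the wording will be needed at least once cannot be asserted: under the illustrative rates the chance in Cohort 2 runs from 49% to 97%. The REEF-1 figure of around 5% in Protocol 2.2.2.1 should not be read as an estimate, because it covers hematologic findings of any grade, mostly mild to moderate, and comes from regimens without PegIFN-α2a.

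A reader might infer that the primary result is undermined, or that ITT is wholly untouched. Neither follows. The ITT definition does not change, but membership can if a stop falls in induction. The effect on the primary estimate is likely minor, about 0.11 points per excluded non-responder under the assumptions shown. The case for acting rests on participant safety and consistent conduct. Which clinical rule is right is not a question for this review.

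**What to change.** Reconcile Protocol 7.1, 8.3.6.4 and 6.6 Table 4 on confirmed Grade 3–4 hematologic abnormalities, including how the PegIFN-α2a restart note applies once a value is confirmed. Reconcile 8.1 with 7.1 on confirmed breakthrough. Each trigger should carry one instruction per drug and phase, and the sponsor's clinical team chooses it. In SAP Attachment 1, apply sequence 58 only where the reconciled protocol required stopping.

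The cost is wording in four protocol sections and one SAP row, with no new procedures. Attachment 1 is in any case to be finalized before the primary analysis database lock.

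SAP Amendment 4 (1 April 2024) suggests that dosing may already be complete. If so, protocol wording no longer helps. The SAP should state which reading sequence 58 uses, and one listing should show each confirmed Grade 3–4 hematologic abnormality with its study phase and the action taken for each drug.

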the participant should discontinue JNJ-3989 and PegIFN-α2a and should be monitored on a weekly basis or as per good clinical practice until ALT and AST levels have returned to <5x ULN, HBV DNA is <20,000 IU/mL, and, if present, liver-related symptoms have improved. NA treatment should be continued. Additional tests can be considered based on clinical judgement (Refer to Section 10.6, Appendix 6, Intervention-emergent ALT/AST Elevations).

In case of prolonged ALT elevation >3x ULN AND >2x nadir, which lasts at least 12 weeks, the decision to continue JNJ-3989 and PegIFN- $\alpha$ 2a should be based upon virologic parameters (eg, HBsAg, HBV DNA) and should be made in consultation with the sponsor.

PegIFN- $\alpha$ 2a may need to be discontinued in clinically significant cases of ALT increase or in combined increase of ALT and direct bilirubin. Refer to the prescribing information for PegIFN- $\alpha$ 2a. 

The NA re-treatment criteria and monitoring after stopping of NA are presented in Section 6.6.2.

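### For an ALT rise with raised direct bilirubin, Section 7.1 requires PegIFN-α2a to stop at once, while Section 8.3.6.2 can leave the stop optional

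*Protocol*

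**What the plan says.** Protocol Section 7.1 opens by saying "All the discontinuation criteria are listed below and the intervention-specific criteria are highlighted". Its main list, which covers JNJ-3989 and PegIFN-α2a together, deals with transaminases by cross-reference: "The participant has ALT/AST elevations, as described in Section 8.3.6.2, Intervention-emergent ALT/AST Elevations". A second list, for PegIFN-α2a alone, is introduced as additional to the first. It says that PegIFN-α2a "during consolidation phase must immediately be discontinued for any of the following reasons", and one entry reads "Participant develops evidence of hepatic decompensation during treatment, or ALT increase clinically significant or accompanied by direct bilirubin increase".

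Section 8.3.6.2 has four relevant parts:

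- After a confirmatory visit that shows an "isolated ALT/AST elevation (ie, with stable albumin, bilirubin [total and direct], and INR) the participant may continue study intervention".
- For confirmed ALT above 1,000 U/L and at least 3x baseline, JNJ-3989 and PegIFN-α2a "should be discontinued unless dynamics of the ALT elevation are indicating improvement towards resolution of the flare".
- When ALT and/or AST is at least 3x ULN and at least 3x nadir, the participant should stop both drugs if any one of a list of findings is present. One is "direct bilirubin >1.5x ULN, OR". The others are INR of 1.5 or more, albumin below 3.0 g/dL, liver-related signs or symptoms, and a catch-all for other evidence of impaired liver function.
- Near the end it says PegIFN-α2a "may need to be discontinued in clinically significant cases of ALT increase or in combined increase of ALT and direct bilirubin", and points to the prescribing information.

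Section 8.3.6.2 refers out to Appendix 6, Section 6.6.2 and the prescribing information, but not to Section 7.1. The benefit-risk text in Section 2.3.3 describes the ALT rules as strict and cites 8.3.6.2 for them.

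**The concern.** This is a liver-safety stopping rule for one drug, stated at two strengths. The weaker statement is in the section that a site opens when ALT rises. An investigator working from 8.3.6.2 alone could reasonably go on giving weekly PegIFN-α2a to a participant for whom 7.1 requires an immediate stop.

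The protocol expects the situation to arise. Section 2.3.2.1 reports that large ALT rises during hepatitis B therapy have sometimes come with raised bilirubin. Section 2.3.3 says that the effect on ALT of adding PegIFN-α2a to JNJ-3989 is unknown.

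There is a minor effect on analysis. SAP Attachment 1, item 58, removes from the per-protocol set anyone who met a discontinuation criterion and was not stopped. That classification depends on which section governs.

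**Working it through.** No arithmetic applies. The check is to put the two sections side by side for each type of ALT rise during consolidation and see whether they give the same instruction for PegIFN-α2a.

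| Situation | Section 7.1, PegIFN-α2a list | Section 8.3.6.2 | Same instruction? |
|---|---|---|---|
| 1. ALT/AST ≥3x ULN and ≥3x nadir, direct bilirubin >1.5x ULN | Stop immediately | Should stop both drugs | Yes in effect |
| 2. ALT/AST as in 1, direct bilirubin increased but ≤1.5x ULN, no other listed finding | Stop immediately | Stop may be needed | No |
| 3. ALT increased but not both ≥3x ULN and ≥3x nadir (nor AST), direct bilirubin also increased | Stop immediately | Stop may be needed | No |
| 4. Isolated ALT rise; bilirubin, albumin and INR stable | Stop immediately if clinically significant | May continue | Depends on judgement |
| 5. Confirmed ALT >1,000 U/L and ≥3x baseline, improving, bilirubin stable | Stop immediately if clinically significant | Exempt from the stop | Depends on judgement |

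Rows 2 and 3 follow from the thresholds. The 7.1 entry asks for an ALT increase accompanied by a direct bilirubin increase and gives no cut-off for either. The firm stop in 8.3.6.2 has a cut-off for both. Between them, the only text in 8.3.6.2 addressed to PegIFN-α2a with combined ALT and direct bilirubin increases is the permissive sentence. The hepatic decompensation entry in 7.1's main list does not fill the gap: absent clinical signs, it needs direct bilirubin above 1.5x ULN together with INR at least 1.5x ULN or albumin below 3.0 g/dL.

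Rows 4 and 5 turn on what counts as clinically significant. Neither section defines the term.

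The wording of 7.1 suggests that its mandatory form is deliberate. Where that section wants a softer rule it says so: virologic breakthrough does not automatically stop treatment, and for mild depression stopping is only to be considered. The ALT entry has no such qualifier.

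**The case against.** The strongest reply is that the protocol, read as a whole, has one answer. Section 7.1 claims to list all the criteria, the PegIFN-α2a list adds to the main one, and a statement that a stop may be needed does not forbid a stop that is required elsewhere. A reader who reaches 8.3.6.2 from 7.1 has already been in 7.1, and Section 2.3.3 also cites Section 7 for withdrawal criteria. This stands as far as it goes: 7.1 appears meant to govern, and both sections can be obeyed together. But 8.3.6.2 does not say so, and a permissive sentence on the same triggers invites a discretion that 7.1 does not give.

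A reader might infer that 8.3.6.2 tells sites to continue PegIFN-α2a when bilirubin is raised. It does not. Its permission for isolated elevations requires stable total and direct bilirubin. The fault is a weaker instruction, not an opposite one. The catch-all finding could also bring some of rows 2 and 3 within the firm stop.

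A reader might also infer that the isolated-elevation and improving-flare allowances contradict 7.1. The documents do not support that. Clinical significance is left to the investigator, and these allowances can be read as guidance on that judgement. The improving-flare exception names PegIFN-α2a expressly. Overriding it would be a clinical trade-off, since Section 2.3.2.2 notes that transaminase rises may indicate immune activation.

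The confirmatory visit, weekly laboratory monitoring and flare review by the DRC and IFLEP reduce the risk, but they do not settle whether the drug must stop. The Appendix 6 flow chart, the Master Protocol and the prescribing information could not be consulted, and any of them might reconcile the wording.

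**Conclusion.** The inconsistency holds for one defined situation: an ALT increase with a direct bilirubin increase that does not meet the firm stop in 8.3.6.2. There 7.1 makes stopping PegIFN-α2a mandatory and 8.3.6.2 makes it optional. No definite conflict is shown for isolated ALT rises, including an improving rise above 1,000 U/L.

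The size can be given only as that band of situations. The documents contain no rate for such events, so no number of affected participants is claimed. The per-protocol consequence is secondary.

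The conclusion assumes that 7.1 states the intended rule, as its opening sentence and unqualified wording suggest, and that Appendix 6 does not already resolve the point. It should be corrected because it concerns liver safety and the correction is nearly free.

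**What to change.** In the PegIFN-α2a sentence of Section 8.3.6.2, replace the permissive verb so that it reads: *must be discontinued, as required by the PegIFN-α2a criteria in Section 7.1*. Check that the Appendix 6 flow chart says the same. Leave the isolated-elevation and improving-flare allowances unchanged, and leave clinical significance to the investigator.

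The cost is one sentence and one check, with no new tests, visits or SAP edits. The downside is that a few participants with a mild bilirubin rise would stop PegIFN-α2a who might otherwise have continued. Section 7.1 already requires that, and it allows a restart in line with the prescribing information.
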